Effectiveness and Safety of Pharmacopuncture Therapy for Chronic Low Back Pain: Study protocol

Protocol ID : JS-CT-2021-02

Clinical trials : NCT04833309

Document Date : September 30, 2021

Study Design and Setting

This two-armed, parallel, multi-center RCT will competitively recruit 100 patients in the Jaseng Hospital of Korean Medicine, Daejeon Jaseng Hospital of Korean Medicine, Bucheon Jaseng Hospital of Korean Medicine, and Haeundae Jaseng Hospital of Korean Medicine. The study protocol was approved by the Institutional Review Board (IRB) of Jaseng Hospital of Korean Medicine before participant recruitment (JASENG 2021-02-012, JASENG 2021-02-013, JASENG 2021-02-014, JASENG 2021-02-032). Additionally, the study protocol will be registered with Clinicaltrials. gov (NCT04833309) and Clinical Research Information Service (KCT0006088) and continuously updated.

Inclusion/Exclusion Criteria

Inclusion Criteria

- LBP onset \geq 6 months
- Numeric rating scale (NRS) score of LBP \geq 5
- Age 19–70 years
- Signing of the ICF to participate in the clinical trial

Exclusion Criteria

- Diagnosis of a serious disease that may cause LBP (eg, spinal metastasis of tumor, acute fracture, spinal dislocation)
- Progressive neurological defects or severe neurological symptoms
- Pain is caused by soft tissue disease rather than the spine (eg, tumor, fibromyalgia, rheumatic arthritis, gout)
- Other chronic diseases that may hinder the interpretation of treatment effects or outcomes (eg, stroke, myocardial infarction, renal disease, diabetic neuropathy, dementia, epilepsy)
- Current use of steroids, immunosuppressants, antipsychotic agents, or other drugs that may affect study outcomes
- Contraindications for pharmacopuncture, including hemorrhagic diseases, anticoagulant usage, severe diabetes mellitus with risk of infection
- Use of drugs that may affect pain, including non-steroidal anti-inflammatory drugs, or pharmacopuncture therapy within the previous week
- Pregnant or breastfeeding women, as well as women planning to conceive
- Lumbar surgery in the previous three months
- Less than one month since participating in another clinical trial or planning to participate in another clinical trial during the study period or follow-up period within 6 months upon enrolment
- Declining to sign a consent form to participate

- Other disqualifications as determined by the investigators

Interventions

Experimental Group: Pharmacopuncture Therapy

Pharmacopuncture therapy will be given two times a week for five weeks. With reference to a study on the current trend in pharmacopuncture therapy that used electronic medical records from 12 Korean medical hospitals,¹¹ the treatment will be performed following the physician's clinical judgment. Additionally, all procedure-related matters will be recorded in patients' charts. Pharmacopuncture procedures will be retrospectively reviewed and recorded in a case report form (CRF) for analysis.

Control Group: Physiotherapy

Based on a study on HIRA data, patients with LBP in Korea are treated using a combination of deep heat therapy, superficial heat therapy, transcutaneous electrical nerve stimulation, and intermittent pelvic traction therapy.¹² According to this data, a physician will choose the method, site, and duration of physiotherapy based on their clinical judgment with respect to the patients' symptoms, radiological findings, and improvement levels. Physiotherapy will be performed twice a week for five weeks; further, all matters regarding the physiotherapy, including the type, duration, and site of physiotherapy, will be recorded in patients' charts. The treatment method will be retrospectively reviewed and recorded in CRF for comparison.

Criteria for Discontinuation and Withdrawal

A participant may be discontinued from the clinical trial for the following reasons: Discovery of a previously undetected disease that may affect study outcomes Request for discontinuation during the study period by the participant or their legal representative or withdrawal of consent by the participant Confirmation of pregnancy during the study period Problems regarding the administration of medical and Korean medical procedures for LBP to the participant Other reasons that warrant discontinuation from the study as determined by the researcher

Concomitant Treatment

Pharmacological therapy and medical care for LBP from another healthcare facility may be permitted during the treatment or follow-up period in case of severe pain. The treatment details and frequency will be recorded in the CRF for analysis.

Outcome

Primary Outcome

NRS score of LBP

The LBP intensity within the previous week will be assessed using the NRS. Patients will be instructed to choose a number from 0–10 that best represents their current discomfort level (0 for no pain, 10 for the worst imaginable pain).

Secondary outcomes

NRS score of radiating leg pain

The intensity of radiating leg pain in the past week will be assessed using the NRS. Patients will be asked to choose a number from 0–10 that best represents their current discomfort level (0 for no pain, 10 for the worst imaginable pain).

Visual analog scale (VAS) score of low back pain and radiating leg pain

The VAS represents the patient's pain level, where one end of a 100-mm line refers to no pain while the other end indicates the worst imaginable pain. Patients are instructed to indicate their intensity of LBP and radiating leg pain within the previous week by marking a point on the line.

Oswestry disability index (ODI)

The participants' functional status will be assessed using the ODI, which is a 10-item tool developed to assess LBP-caused disability. Each item is divided into six steps; further, it is rated on a scale from 0–5. A higher score indicates a more severe disability. We will use the Korean version of the ODI questionnaire, which has been shown to be reliable and valid.

Korean version of the Roland–Morris disability questionnaire (RMDQ)

The RMDQ is among the most widely used tools for evaluating the functional state of patients with LBP. It comprises 24 items, with the patient marking the specific activities limited by their LBP. A positive response scores 1 point, and the questionnaire is scored from 0 (minimal disability) to 24 (severe disability). We will use the questionnaire of the Korean-adapted version, which has been shown to be reliable and valid.

Patient Global Impression of Change (PGIC)

The PGIC is a self-reported tool for patients' improvement levels: 1, very much improved; 2, much improved; 3, minimally improved; 4, no change; 5, minimally worse; 6, much worse; or 7, very much worse. A consistent relationship between the change in NRS and the PGIC was demonstrated regardless of study, disease type, age, sex, study result, or treatment group.

Short Form-12 Health Survey (SF-12) version 2

The SF-12 is a questionnaire for evaluating health-related quality of life. It comprises 12 items in 8 domains: physical functioning, role-physical, bodily pain, general health, vitality, social functioning, role-emotional, and mental health. It usually takes less than five minutes to complete the questionnaire, with a higher score indicating a better health-related quality of life. We will use the Korean version SF-12, which has been shown to be reliable and valid.

5-level EuroQol-5 dimension (EQ-5D-5L)

The EQ-5D-5L is the most widely used indirect evaluation tool for the health state. The descriptive system comprises five dimensions: mobility, self-care, usual activities, pain/discomfort, and anxiety/depression. Each dimension has 5 levels: no problems, slight problems, moderate problems, severe problems, and extreme problems. The patient is asked to indicate their health state by ticking the box next to the most appropriate statement in each of the five dimensions. This decision results in a 1-digit number that expresses the level selected for that dimension. The digits for the five dimensions can be combined into a 5-digit number that describes the patient's health state. There are specific weights for the level of each category; moreover, these weights and constant numbers are used to compute the preference score. We

will use the questionnaire of the Korean-adapted version, which has been shown to be reliable and valid.

Credibility and Expectancy

Participants' expectations for the treatment will be assessed using a 9-point Likert scale. At the enrolment visit, the participants will respond to the question, "How much pain relief do you expect from the pharmacopuncture therapy and physiotherapy? (1 = not at all, 5 = somewhat, and 9 = very much)

Cost Analysis

Cost analysis will be performed using a structured questionnaire for official/unofficial medical costs, nonmedical expenses, time costs, and cost of productivity loss. The official medical cost refers to the cost spent utilizing healthcare facility services, while the unofficial medical cost refers to the cost spent on purchasing health supplements and medical equipment. Non-medical expenses refer to the cost incurred while utilizing healthcare, including transportation, patient's time, and caregiver cost. Cost of productivity loss refers to the cost incurred by lost productivity due to absenteeism and presenteeism due to the disease. The work productivity and activity impairment questionnaire will be used to determine productivity loss; additionally, this will be converted to cost for cost-effectiveness analysis.

Drug Consumption

The types and doses of drugs (rescue drugs) taken for LBP during the study period will be surveyed and recorded at each visit. The frequency of other treatment types, including physiotherapy and injections, will be recorded.

Adverse Events

For safety evaluation, hematology tests (white blood cell [WBC], neutrophil, lymphocyte, monocyte, eosinophil, basophil, red blood cell [RBC], hemoglobin [Hgb], hematocrit [Hct], mean corpuscular volume [MCV], mean corpuscular hemoglobin [MCH], mean corpuscular hemoglobin concentration [MCHC], platelet, erythrocyte sedimentation rate [ESR]), clinical chemical tests (T-protein, albumin, T-bilirubin, aminotransferase [ALT], aspartate aminotransferase [AST], *r*-glutamyl transpeptidase [GTP], blood urea nitrogen [BUN], creatinine), and immunologic tests (C-reactive protein [CRP]) will be performed before and after treatment for both groups to compare the incidence of adverse events.

Adverse events refer to undesirable and unintended signs, symptoms, or diseases that occur after the procedure, including events that may not be caused by the procedure. In this study, data regarding adverse events are collected based on patients' reports and investigators' observations. Further, we will analyze the incidence of adverse events, abnormal laboratory parameters, and serious adverse events suspected to be related to the treatment. The causality between the treatment and adverse events will be assessed using a 6-point scale following the World Health Organization-Uppsala Monitoring Centre causality assessment system (1, definitely related; 2, probably related; 3, possibly related; 4, probably not related; 5, definitely not related; and 6, unknown). The severity of all adverse events will be classified into three categories based on the Spilker classification: Mild (1), treatment not required without marked hindrance of normal everyday life (function); Moderate (2); significantly hinders normal

everyday life (function) with possible treatment being required and subsequent treatment; Severe (3): serious adverse event requiring advanced treatment and leaving sequelae.

Sample Size Calculation

A pilot study was conducted to compare the effectiveness of pharmacopuncture and physiotherapy in patients with chronic LBP. The between-group difference in the mean reduction of the NRS score for LBP was 1.37 ± 1.94 at the primary endpoint, which is immediately after the 5-week treatment; further, Cohen's d was calculated as 0.71. The correlation between the baseline and endpoint was 0.53. Given a significance of 95% and power of 90%, the sample size was calculated to be 64. Considering a 30% withdrawal rate and the recruitment of participants from four facilities, we aim to recruit 100 patients.

Recruitment

Participants will be recruited using a press release, advertisement posters at the clinical trial facility, and online recruitment sites.

Randomization and Allocation Concealment

A statistician will randomize patients into two groups at the same ratio (50 persons for each) using a randomization table on R studio 1.1.463 (© 2009-2018 R Studio, Inc.). The random sequence will be performed using block randomization; further, the size of each block will be randomly set to 2 or 4. The randomization results will be placed in a sealed opaque envelope and stored in a double-locked cabinet by a third person not involved in the study. The coordinator at each study facility will open the envelope for group allocation. Only participants who provide an ICF will be randomly assigned. The randomization number assigned to each participant will be recorded in the electronic medical record.

Blinding

Since blinding the practitioner administering the treatment and the participants is impossible due to the nature of the intervention, only the outcome assessors will be blinded. Outcome-assessors not involved in the procedure and blinded from the group allocation will perform the assessment before the procedure in an isolated space.

Data Collection and Management

We will use an e-CRF using the Internet-based Clinical Research and Trial management system (iCReaT). The principal investigator will train the outcome assessors and investigators of each facility on the standard operating procedure (SOP) as a reference for the study procedures, including writing a CRF and entering data. A query will be issued for a range check of data values. Data entered into the e-CRF will be cleaned and locked to prevent access by investigators other than the one in charge of data management.

Statistical Methods

We will perform both intention-to-treat (ITT) and per-protocol (PP) analyses, with ITT as the primary analysis. For the PP analysis, we will include participants who complete at least seven treatment sessions over 5 weeks. Missing data will be handled by multiple imputation (MI) for analysis of covariance (ANCOVA) and comparison of area under the curve (AUC), as well as

the mixed model for repeated measures for the linear mixed model. For survival analysis, outcomes after the missing time point will be censored. For sensitivity analysis, the last observation carried forward (LOCF) will be used for missing data imputation; further, the normality of distribution will be tested. Nonparametric data will be analyzed using the Wilcoxon-rank sum test. Sociodemographic characteristics and treatment expectancy of the participants will be assessed according to the group. Continuous variables will be presented as mean (SD) or median (quartile), with between-group differences being analyzed using Student's t-test or Wilcoxon-rank sum test, depending on their distribution. Categorical variables will be presented as frequency (%) and analyzed with the chi-square test or Fisher's exact test.

The study endpoints are the differences in the extent of changes in continuous outcomes (NRS, VAS, NDI, NPQ, EQ- 5D-5L, SF-12) at each time point from the baseline. As the primary analysis, we will use a linear mixed model with the covariant factors significantly different from the baseline as covariates and the group as the fixed factor. Next, ANCOVA will be performed on sets processed by MI and LOCF.

To compare the total difference in each outcome within a certain period (treatment period and total study period), the AUC will be calculated for each time point after randomization and compared using Student's t-test. Further, the proportion of patients whose NRS and VAS scores dropped by > 50% from the baseline values will be compared at each time point. The time from randomization to lumbar recovery, which was defined as > 50% reduction in the pain indices, will be compared using Kaplan-Meier survival analysis. Further, the curves will be compared using the Log rank test. Additionally, hazard ratios will be compared using the Cox proportional hazard model. The significance level will be set at 0.05 for all analyses. All statistical analyses will be performed using the SAS 9.4 (© SAS Institute, Inc., Cary, NC, USA) or R studio 1.1.463 (© 2009-2018 RStudio, Inc.) software. Statistical significance will be set at $p < 0.05$.

In case the superiority test fails, a non-inferiority test will be performed. The non-inferiority margin will be set to -1 (NRS), which represents half of the minimal clinically important difference. Pharmacopuncture will be considered non-inferior to physiotherapy if the lower bound of the 95% confidence interval (CI) of the between-group difference of the NRS score reduction does not exceed the non-inferiority margin.

Data Monitoring

The monitoring staff will supervise the clinical trial process, as well as periodically review and confirm whether the study is performed and recorded according to the protocol, SOP, clinical trial management standards, and applicable regulations. The clinical trial will be monitored by the monitoring staff of each clinical trial facility and the sponsor institution using periodic visits and phone calls. At the monitoring visits, the monitoring staff will check the original participant records and data storage (study files). Further, they will inspect the clinical trial procedure and discuss any problems with the investigators.

In case of unexpected or unacceptable risks to participants or occurrence of serious adverse events related to pharmacopuncture or physiotherapy in $\geq 25\%$ of the participants, the clinical trial may be paused. The analysis will be only accessed by the statistician and principal investigator; additionally, the final decision to terminate the study will be made by the principal

investigator

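### Discontinuation is defined only as leaving the trial, and nothing in the plan keeps participants who stop treatment without withdrawing consent in the week-5 pain assessment that the primary ITT analysis needs

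*Combined protocol and SAP*

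**What the plan says.** All references are to the combined protocol and SAP. Week-5 NRS below means the low back pain NRS at the primary endpoint, which Sample Size Calculation places directly after the five weeks of treatment.

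- **Criteria for Discontinuation and Withdrawal.** The opening line is "A participant may be discontinued from the clinical trial for the following reasons". One reason concerns delivery of treatment: "Problems regarding the administration of medical and Korean medical procedures for LBP to the participant". The last is a catch-all, again at study level: "Other reasons that warrant discontinuation from the study as determined by the researcher". The list also contains pregnancy and a newly discovered disease. A participant's request to discontinue shares one item, and one consequence, with "withdrawal of consent by the participant".
- **Statistical Methods.** "We will perform both intention-to-treat (ITT) and per-protocol (PP) analyses, with ITT as the primary analysis". For the PP set, "we will include participants who complete at least seven treatment sessions over 5 weeks". Gaps are handled by a mixed model in the primary analysis, by multiple imputation for ANCOVA and AUC, by LOCF as sensitivity analysis, and by censoring in the survival analysis.
- **Sample Size Calculation.** "Considering a 30% withdrawal rate and the recruitment of participants from four facilities, we aim to recruit 100 patients".
- **Adverse Events.** Laboratory tests "will be performed before and after treatment for both groups to compare the incidence of adverse events".
- **Blinding.** Participants and practitioners are not blinded; outcome assessors are.

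No section describes an early-termination visit, or continued outcome assessment after discontinuation.

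**The concern.** An ITT comparison needs the outcome of everyone randomized, including those who stopped treatment. Here the only event defined for stopping is departure from the trial, and it applies to reasons that do not stand in the way of a pain score. The primary endpoint and the second laboratory sample are both timed by the end of treatment, so a site has no stated time point for a participant whose treatment ends early. Four sites may resolve this in different ways.

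What is at stake is bias in the primary comparison. The mixed model and multiple imputation rely on missing values being predictable from observed ones. That is doubtful when someone is removed because of a treatment problem or a new disease. Since treatment is open and one reason rests on the researcher's judgement, removals can also differ by arm. The other analyses do not repair this: LOCF carries an earlier score forward, the PP set leaves out anyone who stopped before seven sessions, and the survival analysis censors.

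**Working it through.** **1. The plan's sample size.** Inputs from Sample Size Calculation: difference 1.37, SD 1.94, baseline-endpoint correlation 0.53, power 90%. Alpha is 0.05; two-sided testing is assumed because sidedness is not stated.

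- d = 1.37 / 1.94 = 0.706 (the plan gives 0.71).
- Normal approximation, per arm: 2 × (1.960 + 1.282)² × (1 − 0.53²) / 0.706² = 30.3, so 31 per arm and 62 in total.
- The t-based version gives 31.3, so 32 per arm and 64 in total. This matches the plan.
- Allowance for withdrawal: 64 / (1 − 0.30) = 91.4, or 92. The step to 100 is the plan's stated allowance for four facilities.

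**2. Power.** At 30% withdrawal, 100 × 0.70 = 70 are observed (35 per arm), more than 64. Power at 1.37 with baseline adjustment is 93.6% (normal) or 93.0% (t). The sample size is sound on the plan's own terms.

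**3. Size of a possible shift.** Let p be the share of an arm with no week-5 NRS, and δ the amount by which their true mean is worse than the imputed mean. The between-group difference is off by p₁δ₁ − p₂δ₂. Equal shares and equal departures cancel: 0.30 × 1 − 0.30 × 1 = 0. Differences between arms are therefore what matters. The documents give neither p by reason nor δ. Assume δ = 1 NRS point in one arm and no departure in the other:

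| Share of one arm removed | Participants (of 50) | Shift | Share of 1.37 | Share of the non-inferiority margin of 1 |
|---|---|---|---|---|
| 10% | 5 | 0.10 × 1 = 0.10 | 7% | 10% |
| 20% | 10 | 0.20 × 1 = 0.20 | 15% | 20% |
| 30% | 15 | 0.30 × 1 = 0.30 | 22% | 30% |

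The shift is proportional to δ, so half a point would halve each figure. The 30% row takes the whole withdrawal allowance, which the plan does not tie to the listed reasons. Part of it may be consent withdrawal or loss to follow-up, where no value could be obtained.

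**4. Effect of keeping these participants.** Assume all 100 are followed and those who stop treatment show no between-arm effect. The expected difference is (1 − share stopping) × 1.37, with 50 per arm and baseline adjustment (normal approximation):

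| Share stopping | Difference | Power |
|---|---|---|
| 10% | 1.23 | 96.3% |
| 20% | 1.10 | 91.5% |
| 30% | 0.96 | 83.0% |

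**The case against.** The strongest reply is that the gap is one of wording. A reader might infer that everyone who meets a listed reason must leave, and that the trial then collects no NRS and no bloods on them. The documents do not say so. The rule is permissive, no section forbids further assessment, and the second laboratory sample can be read as due after the last treatment received, whenever that is. Adverse events are also collected from patient reports and investigator observation, so they do not depend on that sample alone. Data Collection and Management refers to an SOP that is not part of the documents. The PP rule implies that people with fewer than seven of the ten planned sessions (2 × 5) can remain in ITT, and Concomitant Treatment allows outside care for severe pain, so poor pain control need not mean exit. All of this stands against the strong reading. It does not close the gap: the PP rule deals with missed sessions and is silent on participants who have been discontinued.

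A reader might also infer that the missing outcomes will come mainly from patients whose treatment failed or was not tolerated, or that 30 of 100 will lack the endpoint for the listed reasons. The list names neither lack of effect nor adverse events, and the 30% is a general allowance. Neither inference is supported.

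Finally, off-treatment values can dilute the effect, down to 0.96 in the last row of step 4. That is a real cost, but the diluted quantity is what an ITT analysis is meant to estimate.

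**Conclusion.** The point holds in limited form. The plan defines discontinuation only at trial level, applies it to reasons that leave the pain score obtainable, and nowhere keeps those participants in assessment. A site that follows the text can lose week-5 NRS values that could have been observed, and the ITT result then leans on missing-at-random or LOCF.

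The size is illustrative: 0.10 to 0.30 NRS points under the assumptions of step 3, with 0.30 as the upper illustration. The documents cannot show that a shift of this size is likely, or in which direction it would go. The sample size and the power are not in question. The point should be settled before assessments are missed, because a week-5 score cannot be recovered later.

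On the laboratory tests, the documents support only this: the before-and-after wording has to be reconciled with treatment that ends early. They give no basis for this review to set the timing of the sample.

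**What to change.** In Criteria for Discontinuation and Withdrawal, separate two events: discontinuation of study treatment, and withdrawal of consent to further assessment. State that participants who stop treatment without withdrawing consent to assessment keep the scheduled outcome and adverse-event assessments, at minimum the week-5 low back pain NRS taken by the blinded assessor. In Statistical Methods, state that these values enter the ITT analysis. In Adverse Events, say how the laboratory wording applies when treatment ends early; the investigators should decide the timing.

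The change alters no rule on who stops treatment, and neither 64 nor 100 changes. It costs protocol and consent wording, some contact effort, possibly a different mode of NRS collection for a few participants (with care to keep the assessor blinded), and some dilution of the estimated effect, as in step 4.

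### The only serious adverse event analysis named in the plan is restricted to events suspected to be treatment-related, with no causality assessor, blinding status or category rule stated

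*Combined protocol and SAP*

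**What the plan says.** The Adverse Events section defines an adverse event without regard to cause, "including events that may not be caused by the procedure". The data come from what patients report and what investigators observe. The planned analysis is given in one sentence: "we will analyze the incidence of adverse events, abnormal laboratory parameters, and serious adverse events suspected to be related to the treatment".

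Three other statements in that section bear on the point:

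- Laboratory tests "will be performed before and after treatment for both groups to compare the incidence of adverse events".
- "The severity of all adverse events will be classified into three categories".
- "The causality between the treatment and adverse events will be assessed using a 6-point scale", running from 1 (definitely related) to 5 (definitely not related), with 6 for unknown.

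The Blinding section says: "Since blinding the practitioner administering the treatment and the participants is impossible due to the nature of the intervention", and that "only the outcome assessors will be blinded". The Statistical Methods section contains no adverse event analysis.

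**The concern.** Randomisation makes the arms comparable for the incidence of serious events from any cause. It does not do so for events selected afterwards by a judgement of cause, if that judgement can be influenced by knowing the treatment. The two treatments look different: one is an injection, the other is heat, electrical stimulation or traction. An event could be attributed to a needle more readily than to a heat pack, or less readily by someone who favours pharmacopuncture. The direction cannot be known in advance.

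If the filter operates differently in the two arms, the reported serious-event comparison can show a difference that does not exist or hide one that does. A serious event judged unrelated, or that nobody can attribute, would still be counted among adverse events in general, but the reader would not see that it was serious. The protocol title puts safety beside effectiveness, so the serious-event table will be read as a main safety result.

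**Working it through.** The plan states no figure on this point, so there is nothing to reproduce. The check is mainly a reading of the text, followed by an illustration of scale.

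**1. What the qualifier covers.** The sentence lists three items and ends with the relatedness qualifier. Grammatically it could attach to the last item or to all three. The all-cause definition, the laboratory comparison in both groups without a filter, and the grading of every adverse event for severity all favour attaching it to the last item only. On that reading, adverse event incidence and laboratory abnormalities are unfiltered and serious events are filtered. No reason is given for treating serious events differently.

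**2. Whether another section supplies an all-cause serious-event analysis.** Statistical Methods covers the efficacy outcomes, the intention-to-treat and per-protocol sets, missing data and non-inferiority, but not adverse events. Severity grading applies to every event, but it is a classification and no comparison of grades by arm is promised. The top grade is also tied to sequelae, so it need not capture every serious event. Data Monitoring mentions serious events in a criterion for pausing the trial, and that too is tied to relatedness. No all-cause serious-event table is named anywhere.

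**3. Who applies the filter.** Practitioners and participants are unblinded and outcome assessors are blinded. The causality sentence is in the passive and names no judge. Nothing gives the blinded assessors this task, and nothing says that an unblinded investigator has it.

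**4. What passes the filter.** The six categories are not mapped to suspected or not suspected. Categories 1 to 3 (definitely, probably, possibly related) would presumably count, and 4 and 5 would not. Category 6 (unknown) has no assignment, so it could be settled after the events are known.

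**5. Scale, for the serious-event item only.** Inputs:

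- n = 50 per arm (Randomization and Allocation Concealment section).
- r = true serious-event rate, equal in both arms. Not in the documents; assumed 2% to 6%.
- a and b = share of serious events judged related in the two arms. Not in the documents; assumed from 50%/50% to 90%/10%.

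Expected all-cause events per arm = n × r. Expected filtered events = n × r × a in one arm and n × r × b in the other. The apparent ratio is a / b, because n and r cancel.

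| r | All-cause, each arm | Filtered, 50%/50% | Filtered, 70%/30% | Filtered, 90%/10% |
|---|---|---|---|---|
| 2% | 50 × 0.02 = 1 | 0.5 vs 0.5 | 0.7 vs 0.3 | 0.9 vs 0.1 |
| 4% | 50 × 0.04 = 2 | 1.0 vs 1.0 | 1.4 vs 0.6 | 1.8 vs 0.2 |
| 6% | 50 × 0.06 = 3 | 1.5 vs 1.5 | 2.1 vs 0.9 | 2.7 vs 0.3 |
| Ratio | 1 | 1 | 0.7 / 0.3 = 2.3 | 0.9 / 0.1 = 9 |

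Reversing the attribution shares reverses the ratio. With equal attribution the filter does not distort the ratio, although it halves the counts at 50%/50%. The expected counts are too small for a meaningful test with or without the filter.

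**The case against.** The strongest reply is that the plan already contains most of what is wanted. Adverse events are defined regardless of cause and their incidence is to be analysed. Laboratory tests are compared in both groups without a filter, and every event is graded for severity. A serious event judged unrelated is therefore counted. This stands, and it rules out a stronger reading: a reader might infer that the whole safety analysis, or the whole comparison of harms between arms, is confined to related events. The documents do not support that. The analysis sentence itself names two other items, and the surrounding text favours leaving those unfiltered.

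A second reply is that unblinded attribution is an inference. This also stands in part. The plan does not say that causality is judged by someone who knows the allocation, and equally it does not say that it is not. The defect is that the assessor and blinding status are unspecified, in a trial where the people closest to the events are unblinded.

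A third reply is that serious events will be few and the top severity grade will show them anyway. The first half is probably right and limits the size of the point. The second half does not hold, because that grade requires sequelae and no by-arm table of grades is planned.

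Finally, all-cause counts are not immune either. Events come from patients and investigators, so reporting may also differ by arm. Removing the filter takes away dependence on attribution, not dependence on reporting.

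**Conclusion.** The point holds for the serious-event item. The plan states a rule that selects serious events on suspected relatedness, and leaves the causality assessor, the blinding and the category mapping undefined. No other section supplies an all-cause serious-event comparison by arm. The remaining adverse event and laboratory analyses are, on the natural reading, unaffected, although the sentence should be reworded so that this does not rest on grammar.

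The size is modest. Under the assumed 2% to 6% rate, 1 to 3 serious events are expected per arm and the comparison is descriptive. The 2.3-fold and 9-fold ratios show what differential attribution could do. They are not estimates of what it will do, and they rest wholly on assumed rates and attribution shares. They should not be carried over to overall adverse event incidence, which is not filtered. With so few events, one event dropped or kept visibly changes the table, which is the practical reason to settle the rule beforehand. The efficacy conclusions are not touched.

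**What to change.** Reword the analysis sentence in the Adverse Events section along these lines: *The incidence of all adverse events, all abnormal laboratory parameters and all serious adverse events will be compared by arm regardless of causality. Events in causality categories 1 to 3 will be shown by arm in a secondary table; category 6 (unknown) will be counted as related in that table.* Counting unknown as related is one workable convention. What matters is that some rule is fixed before the data are seen.

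Add one sentence saying who assigns causality and whether that person is blinded to allocation, and repeat or cross-reference the analysis in Statistical Methods.

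The events and causality codes are already to be collected, so the cost is wording and one extra table. The only drawback is that all-cause counts include background illness and will be slightly higher than the filtered ones; the secondary table lets the reader see both.
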